10.1 ADVERSE EVENTS

Adverse events will be coded by system organ class and preferred term using the *Medical Dictionary for Regulatory Activities*, version 20.1 or newer.

An AE will be considered a treatment-emergent adverse event (TEAE) if it was present one or after the first application of study treatment or was present before the date of the first application of study treatment and increased in severity or became serious on or after the first application of study treatment.

An AE will be considered a treatment-emergent serious AEs (TESAE) if it is a TEAE that additionally meets any SAE criteria.

The number and percentage of patients reporting TEAEs and treatment-related TEAEs in each treatment group will be tabulated by system organ class and preferred term, separately. If more than 1 AE is coded to the same preferred term for the same patient, the patient will be counted only once for that preferred term using the greatest severity.

A summary table will be provided for subjects with TEAE, TESAE, death and subjects with TEAEs leading to discontinuation if 5 or more participants reported such events. A subject listing of all AEs will be presented.

11.0 **INTERIM ANALYSIS**

No interim analysis is planned for this study.

12.0 **DETERMINATION OF SAMPLE SIZE**

As this is a proof of concept study, no formal calculation of sample size was conducted. Approximately 70 participants will be enrolled to achieve approximately 60 completed.

13.0 **STATISTICAL SOFTWARE**

Statistical analyses will be performed using version [REDACTED]
[REDACTED]

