9.0 ADVERSE EVENTS

An AE is defined as any unfavorable and unintended sign (including an abnormal laboratory finding) symptom, or disease temporally associated with the use of an investigational product but not necessarily related to the investigational product. An AE may also be called a complication. The capture of AEs will begin with the participant's entry into the study.

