9.3 Relationship of the AE to the investigational device

Definite	A clear-cut causal relationship with the study device and no other possible cause
Probable	A causal relationship with the study device is likely although alternate etiologies are also possible
Possible	A causal relationship with study device is not definite, alternate etiologies are also possible
Not related	The AE has no causal relationship to study device and/or there is evidence of alternative etiology such as concurrent medication or illness.
Not applicable	The participant has not been exposed to the study device.

The AE will be determined to be device related, making it an adverse device effect (ADE), if it is identified to have had a definite, probable or possible causal relationship to the study device.

An AE is unanticipated if the nature, severity, or frequency of the event is not consistent with either the known or foreseeable risk of AEs associated with the procedures involved in the research that are described in (a) the protocol-related documents, such as the IRB-approved research protocol, user manuals and the current IRB-approved informed consent document, and (b) other relevant sources of information such as product labeling and package inserts; or the expected natural progression of any underlying disease, disorder, or condition of the participant(s) experiencing the AE and the participant’s predisposing risk factor profile for the AE.

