14.5 MISSING SEVERITY ASSESSMENT FOR ADVERSE EVENTS

If severity is missing for an AE that started before the date of the first dose of study treatment, an intensity of mild will be assigned. If severity is missing for an AE that started on or after the date of the first dose of study treatment, an intensity of severe will be assigned. The imputed values for severity assessment will be used for the incidence summary; the values will be shown as missing in the data listings.

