14.6 MISSING CAUSAL RELATIONSHIP TO STUDY TREATMENT FOR ADVERSE EVENTS

[If the 3-point scale for relationship to study treatment is used (ie, “Not related,” “Possibly related,” and “Related”), the relevant text below may need to be modified accordingly. For example, “causal relationship” would become “relationship” and “yes” would become “*related*.”]

If the causal relationship to the study treatment is missing for an AE that started on or after the date of the first dose of study treatment, a causality of yes will be assigned. The imputed values for causal relationship to study treatment will be used for the incidence summary; the values will be shown as missing in the data listings.

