14.7 MISSING DATE INFORMATION FOR ADVERSE EVENTS

The following imputation rules only apply to cases in which the start date for AEs is incomplete (ie, partly missing).

Missing month and day

- If the year of the incomplete start date is the same as the year of the first dose of study treatment, the month and day of the first dose of study treatment will be assigned to the missing fields
- If the year of the incomplete start date is before the year of the first dose of study treatment, *December 31* will be assigned to the missing fields
- If the year of the incomplete start date is after the year of the first dose of study treatment, *January 1* will be assigned to the missing fields

Missing month only

- If only the month is missing, the day will be treated as missing and both the month and the day will be replaced according to the above procedure

Missing day only

- If the month and year of the incomplete start date are the same as the month and year of the first dose of study treatment, the day of the first dose of study treatment will be assigned to the missing day
- If either the year of the incomplete start date is before the year of the date of the first dose of study treatment or if both years are the same but the month of the incomplete start date is before the month of the date of the first dose of study treatment, the last day of the month will be assigned to the missing day
- If either the year of the incomplete start date is after the year of the date of the first dose of study treatment or if both years are the same but the month of the incomplete start date is after the month of the date of the first dose of study treatment, the first day of the month will be assigned to the missing day

If the stop date is complete and the imputed start date as above is after the stop date, the start date will be imputed by the stop date.

If the start date is completely missing and the stop date is complete, the following algorithm will be used to impute the start date:

- If the stop date is after the date of the first dose of study treatment, the date of the first dose of study treatment will be assigned to the missing start date
- If the stop date is before the date of the first dose of study treatment, the stop date will be assigned to the missing start date.

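### The SAP's treatment-emergent rule tests whether an adverse event was present, not whether it began, on or after first application, so unchanged pre-treatment events count

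*SAP*

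**What the plan says.** SAP 10.1 defines a treatment-emergent adverse event (TEAE) by two alternatives. An event qualifies "if it was present one or after the first application of study treatment", or if it "was present before the date of the first application of study treatment and increased in severity or became serious" from the first application onward. A treatment-emergent serious event (TESAE) is a TEAE that also meets a seriousness criterion. The flag feeds the main safety tables: "The number and percentage of patients reporting TEAEs and treatment-related TEAEs in each treatment group will be tabulated" by system organ class and preferred term. It also feeds a summary table that depends on at least 5 participants having such events.

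Events can be recorded before treatment. Protocol 9.0 states that "The capture of AEs will begin with" study entry, and Protocol 9.3 has a *Not applicable* relationship category defined by "The participant has not been exposed to the study device".

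The SAP's other adverse event rules work from the start date:
- **14.5, missing severity:** "If severity is missing for an AE that started on or after the date of the first dose of study treatment", it is set to severe; if the event started earlier, it is set to mild.
- **14.6, missing causality:** a relationship is imputed only when it is "missing for an AE that started on or after the date of the first dose of study treatment".
- **14.7, missing dates:** the start date is placed relative to first dose. For example, when only a later stop date is known, "the date of the first dose of study treatment will be assigned to the missing start date".

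**The concern.** An event that began between study entry and Day 0 and was still ongoing, unchanged, at first application is present after that application. The first clause therefore flags it, although treatment cannot have caused its onset and it did not get worse. No visible text in either document excludes such events from the TEAE count.

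Comparing safety is part of the primary objective. If the rule is programmed as written, TEAE and TESAE counts in both arms would include events that predate any treatment. Background events added to both arms pull the arms' percentages together on average, so the table would tend to understate a real difference. With about 35 participants per arm, a few misclassified participants are visible.

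**Working it through.** The plan gives no figure to reproduce, so the check has two parts: the logic of the rule, and an illustration of its possible size.

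**1. The rule applied to five timing patterns**

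| Pattern | SAP 10.1 as written | Onset-based first clause |
|---|---|---|
| Began and resolved before treatment | no | no |
| Began before, ongoing, unchanged | **yes** | **no** |
| Began before, worsened after | yes | yes |
| Began on Day 0 | yes | yes |
| Began later | yes | yes |

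Only one pattern differs. Under the written rule the second clause adds nothing in any pattern, because an event that worsens after first application is already present after it.

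**2. Fit with the missing-data rules**

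- A TEAE with pre-treatment onset and missing severity would be set to mild under 14.5.
- One with missing causality would have no imputation rule, because 14.6 covers only events starting on or after first dose.
- For an event that began earlier, presence at first application depends on its stop date. SAP 14.7 imputes only adverse event start dates; stop-date imputation is given only for medications (14.8.2).

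The SAP therefore supplies the date handling that an onset rule needs, but not what a presence rule needs.

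**3. Window for such events**

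Participation lasts about 44 days (Protocol 8.10) and treatment about 30 days (Protocol 4.0): 44 − 30 = about 14 days, if study entry means Screening.

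**4. Illustrative size**

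Inputs from the documents: about 70 participants randomized 1:1, so 70 / 2 = 35 per arm. Everything else is assumed:
- q is the share of participants with an event that began before treatment and continued unchanged.
- The true any-TEAE rates are t₁ = 30% (TrueTear) and t₀ = 10% (compress), a difference of 20 points and a ratio of 3.0.
- Background events and new events are independent.

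Formulas:
- Observed rate = q + (1 − q)t
- Observed difference = (1 − q)(t₁ − t₀)
- Participants wrongly added to the any-TEAE row, per arm = 35 × q × (1 − t)
- SD of the chance imbalance in background share between arms = √(2q(1 − q)/35)

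At q = 5%:
- TrueTear: 0.05 + 0.95 × 0.30 = 33.5%
- Compress: 0.05 + 0.95 × 0.10 = 14.5%
- Difference: 0.95 × 20 = 19 points
- Ratio: 33.5 / 14.5 = 2.3
- Added: 35 × 0.05 × 0.70 = 1.2 and 35 × 0.05 × 0.90 = 1.6

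| q | Observed rates | Difference (points) | Ratio | Wrongly added, TrueTear / compress | SD of imbalance (points) |
|---|---|---|---|---|---|
| 2% | 31.4% vs 11.8% | 19.6 | 2.7 | 0.5 / 0.6 | 3.3 |
| 5% | 33.5% vs 14.5% | 19.0 | 2.3 | 1.2 / 1.6 | 5.2 |
| 10% | 37.0% vs 19.0% | 18.0 | 1.9 | 2.5 / 3.2 | 7.2 |
| 20% | 44.0% vs 28.0% | 16.0 | 1.6 | 4.9 / 6.3 | 9.6 |

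The factor (1 − q) on the difference holds for any pair of true rates. The ratio depends heavily on the assumed 10% compress rate.

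The number of participants with at least one wrongly flagged event, whether or not they also have a new one, is 70q: 1.4, 3.5 and 7 at q = 2%, 5% and 10%. The chance of at least one such participant, 1 − (1 − q)⁷⁰, is 76%, 97% and over 99%.

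**The case against.** The strongest reply is that the sentence shows its own intent. It gives events present before treatment a separate clause with its own conditions, and an unchanged event fails them. A careful programmer would read the first clause as new onset, which makes this loose drafting rather than a wrong analysis. That is a fair account of the intent, but it also confirms that the sentence says something else, and a programmer following it literally would produce the wrong flag.

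Other points stand in whole or in part:
- SAP 14.5 to 14.7 are missing-data conventions, not a rival TEAE definition. The mismatch is one of logic, not a direct contradiction.
- Table specifications are in a separate document (SAP 3.0), and SAP 14.2 on derived variables shows only a heading. A derivation could exist that cannot be seen here. Nothing visible cures the wording.
- Study entry is not defined, so the window could be shorter than 14 days. The *Not applicable* category and the mild-severity rule in 14.5 still show that pre-treatment events were expected.
- Nothing in the documents supports q of 10% to 20%. At 2% to 5% the difference moves by 1 point or less, below the chance imbalance of 3.3 to 5.2 points. The ratio, which moves more, is not a planned statistic.
- A false TESAE needs an event that was already serious before Day 0, still ongoing and not worsening, in someone who was nevertheless treated. That should be rare.

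**Conclusion.** The concern holds: the definition is wrong as written, with low impact. Followed literally, SAP 10.1 counts unchanged pre-treatment events as treatment-emergent and makes its own second clause redundant. The size cannot be determined from the documents. Under the assumed 30% and 10% rates, q of 2% to 5% adds roughly 0.5 to 1.6 participants per arm and takes 0.4 to 1 point off a 20-point difference. The pull toward no difference holds only in expectation; in a single trial of this size, chance imbalance in background events could push the comparison either way.

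The reach is limited. Treatment-related TEAEs should be largely unaffected, because pre-exposure events would be classed as *Not applicable* or *Not related* and missing causality is not imputed for them. Rows for device-type events such as nasal discomfort are diluted less than the any-TEAE row. The listing of all adverse events is unchanged. Adverse events are reported as counts and percentages, so no test result changes.

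**What to change.** In SAP 10.1, make the first clause apply to an event that *began* on or after the first application, which also removes the typo. Keep the second clause for earlier events that worsen or become serious, and show unchanged pre-treatment events only in the adverse event listing. This brings 10.1 into line with the start-date logic of 14.5 and 14.6.

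The cost is one phrase in the SAP and one programming condition on the adverse event start date, which 14.7 already imputes when it is incomplete. Study conduct and data collection do not change.

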3.0 INTRODUCTION

This statistical analysis plan (SAP) provides a more technical and detailed elaboration of the statistical analyses of the effectiveness and safety data as outlined and/or specified in the final [protocol](#) of Study 1919-610-019 (version dated June 1, 2017). Specifications of tables, figures, and data listings are contained in a separate document.

[figure not shown]
Study 1919-610-019 is a prospective, open-label, randomized, parallel two-arm study conducted at up to two sites in patients at least 22 years of age who have a Standard Patient Evaluation for Dryness (SPEED) [REDACTED]. In at least one eye, the participants need to meet all of the objective measure in the same eye:

[figure not shown]
- A basal Schirmer test of \geq [REDACTED]
[REDACTED]
- [REDACTED]
- Tear film breakup time (TBUT) [REDACTED]
[REDACTED]

The length of this study will be approximately 44 days. Signed informed consent from the patient will be obtained before any study-related procedures are begun. At the Screening Visit, patients who provide written informed consent will be assigned a screening number. At the day of randomization (Day 0), patients meeting the entry criteria will be randomized (1:1 ratio) to either the TrueTear or moist heat compress control treatment groups. Following the initial application of treatment in clinic at Day 0, participants will apply the randomized treatment for approximately 30 days.

Effectiveness and safety assessments will be conducted at the clinic at Screening, Baseline, Day 7, Day 14 and Day 30.

The schedule of evaluations for Study 1919-610-019 is presented in [Table 3–1](#).

4.0 **OBJECTIVES**

The primary objective of this study is to compare the safety and effectiveness of TrueTear (intranasal tear neurostimulator) to standardized moist heat compress (Thermalon Dry Eye Compress) for the treatment of Meibomian Gland Disease (MGD).

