5.3 DATA COLLECTED BUT NOT ANALYZED

The following variables collected on the CRF but not addressed in the analysis will be listed in the subject data listing without statistical summary or hypothesis testing: dates that informed consent was signed, dates of informed consent version, reason for unscheduled visits; medical status update, and required examination forms.

6.0 **PATIENT DISPOSITION**

The frequency (count and percent) of patients randomized, treated, completed study and prematurely discontinued during the study period will be presented for each treatment group and overall. The number of patients screened will be summarized overall only.

The frequency of patients who complete the study period and of patients who prematurely discontinue during the same period will be presented on the ITT Population. The reasons for premature discontinuation from the study period as recorded on the termination pages of the case report forms will be summarized (number and percentage) by treatment group for the ITT Population. All patients who prematurely discontinue during the study period will be listed by discontinuation reason for the ITT Population.

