10.0 SAFETY ANALYSES

The safety analysis will be performed using the Safety Population. The safety parameters will include adverse events (AEs) and other safety measurements defined in the protocol including corrected distance visual acuity or slip lamp biomicroscopy findings. For each safety parameter, the last nonmissing safety assessment before the first dose of study treatment will be used as the baseline for all analyses. Continuous variables will be summarized by number of patients and mean, SD, median, minimum, and maximum values. Categorical variables will be summarized by number and percentage of patients.

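### Could the five-participant condition in SAP 10.1 keep serious adverse events or deaths out of the safety comparison?

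*SAP*

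**What the plan says.** SAP 10.1 makes one short overview table conditional: it is to be "provided for subjects with TEAE, TESAE, death and subjects with TEAEs leading to discontinuation if 5 or more participants reported such events". The sentence does not define the counting unit, and it does not say that this table is split by arm.

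The same section sets out other output with no threshold. It gives the number and percentage of "patients reporting TEAEs and treatment-related TEAEs in each treatment group will be tabulated by system organ class and preferred term", and a subject listing of all adverse events. An event is a TESAE "if it is a TEAE that additionally meets any SAE criteria", so every TESAE is also in the TEAE table.

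Elsewhere in the SAP:

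- Section 10.0 fixes the analysis set: "The safety analysis will be performed using the Safety Population".
- Section 6.0 covers withdrawals without a threshold. Reasons for stopping early "will be summarized (number and percentage) by treatment group for the ITT Population".
- Section 8.2 provides a listing of treatment assignment.
- Section 3.0 places the display details elsewhere: "Specifications of tables, figures, and data listings are contained in a separate document".

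**The concern.** Safety is half of the stated aim (SAP 4.0: "The primary objective of this study is to compare the safety and effectiveness of TrueTear"), and SAP 9.1 declares no effectiveness measure, so readers will lean on the safety output. For serious events, deaths and withdrawals due to adverse events, one normally expects a count per arm whatever the number, zeros included.

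Here the count appears only if a threshold is passed, and the threshold can be read in several ways that give opposite outputs from the same data. The tables by organ class and preferred term do not replace it, because they are specified by term and not by seriousness or outcome. On a strict reading, the number of participants per arm with a TESAE or a death might appear in no table. Whether it did would depend on the observed data and on the programmer's choice of reading.

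**Working it through.** **Inputs.** SAP 12.0 gives the size: "Approximately 70 participants will be enrolled to achieve approximately 60 completed". Allocation is 1:1 (SAP 3.0), so about 35 per arm. The threshold is 5 (SAP 10.1). The documents give no rate for any adverse event category, so the rates p below are assumptions shown over a range, the same in both arms. There is no planned figure to reproduce.

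**Reading A: five within a category, both arms together.** With X ~ Bin(70, p), the row appears if X ≥ 5. What can be lost is the case 1 ≤ X ≤ 4, because with X = 0 there is no event to summarise. So P(lost) = 1 − (1 − p)^70 − P(X ≥ 5).

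| p | P(X = 0) | P(1 to 4, no row) | P(X ≥ 5, row shown) |
|---|---|---|---|
| 1% | 0.4948 | 0.5045 | 0.0007 |
| 2% | 0.2431 | 0.7436 | 0.0132 |
| 3% | 0.1186 | 0.8222 | 0.0592 |
| 5% | 0.0276 | 0.7004 | 0.2721 |
| 10% | 0.0006 | 0.1582 | 0.8412 |

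The row becomes more likely than not once p exceeds about 6.6%. The zero-event column matters. At 2% the raw chance of no row is 0.2431 + 0.7436 = 0.9867, but about a quarter of that is trials with nothing to report.

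**Reading B: five within a category in at least one arm.** P(row) = 1 − [P(Bin(35, p) ≤ 4)]². This gives 0.0001 at 1%, 0.0013 at 2%, 0.0572 at 5% and 0.4660 at 10%. The chance of at least one event and no row is P(at least 1 of 70) − P(row):

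- 1%: 0.5052 − 0.0001 = 0.5051
- 2%: 0.7569 − 0.0013 = 0.7556
- 5%: 0.9724 − 0.0572 = 0.9152
- 10%: 0.9994 − 0.4660 = 0.5334

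**Reading C: any listed event counts, both arms together.** The relevant rate is now that of any TEAE. P(table) = P(Bin(70, p) ≥ 5), which is 0.8412 at 10% and 0.9992 at 20%. Once the table is produced it carries the TESAE and death rows, however few those are.

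**Reading D: the condition attaches only to discontinuations.** The TEAE, TESAE and death summary is always produced.

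**Which reading fits the sentence.** It describes one table and lists TEAE first. Taking the condition to refer to the whole list gives C. Taking it to refer to the nearest item gives D. A and B need a row-by-row threshold that the sentence does not mention. Protocol 9.6 lists 13 anticipated effects of the device, among them sneezing, headache and nasal discomfort, so five participants with any TEAE is not a demanding bar.

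**What is left under A or B.** Every TESAE is in the by-arm TEAE table and in the listing. Protocol 9.2 has the investigator judge seriousness for each event, so the information is collected. Under A, at most four participants per category need counting by hand. Under B, at most four per arm. Withdrawal reasons are tabulated by arm on the ITT Population. Randomisation and the first in-office application both take place at Visit 2 (Protocol 8.1.5 and 8.3), so that set should be nearly the Safety Population.

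**The case for a change.** The strongest case for a change is that the ambiguity is real and cheap to remove. Two programmers acting in good faith could deliver different safety outputs. No section available here commits unconditionally to a count of participants with a TESAE or death. Rare events are exactly the ones that a threshold suppresses. Under reading A, a split of 4/35 (11.4%, exact 95% interval 3.2% to 26.7%) against 0/35 would have no subtotal. If the natural reading is meant, deleting the condition costs nothing; if another is meant, deletion helps.

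Much of this stands. The counting unit is undefined and an unconditional table would be tidier. But the 4-to-0 example assumes a serious event rate above 11% in one arm over about 30 days, which nothing in the documents supports. Even then the two-sided Fisher p-value is 2 × C(35,4)/C(70,4) = 0.114, and SAP section 10 plans no between-arm test of adverse events that the missing row could affect. The four people would still be visible in the by-arm tables and in the listing. The separate table specifications are also the usual place for a display trigger, and they may already state the rule.

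**Conclusion.** The SAP sentence is unclear, but the gap is one of presentation. On the natural readings the TESAE and death rows appear almost always (0.9992 at an assumed 20% TEAE rate) or always. On the strict per-category reading a subtotal would be missing despite one to four affected participants with probability about 0.50 to 0.82 at assumed rates of 1% to 5%. Even then no event drops out of the tabulated and listed data, and the subtotal can be recovered by a count of a few participants. No estimate, test, sample size or conclusion depends on the reading.

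This rests on about 70 participants at 1:1, on assumed event rates equal in both arms, and on table specifications that were not available. Analysts would be expected to fill the gap sensibly by showing the four counts, and the plan does not need to change for that.
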